6.1.3.1 Model checking procedures

Diagnostic output from the PROC MCMC model will be reviewed.

6.1.3.2 Handling of missing values/censoring/discontinuations

All subjects with a baseline ESSPRI and at least one post-baseline ESSPRI will be included in the primary analysis. The primary analysis method provides unbiased estimates of the treatment effect under the assumption that data are missing at random (MAR). Guidelines for subject discontinuation should ensure that this assumption is reasonable. If a substantial proportion (e.g. more than 15%) of subjects discontinue before week 13 visit, alternative methods to account for missing data may be considered.

Follow up visits from subjects who discontinued will not be included in the analysis.

For patients where treatment was withdrawn PD summary statistics and all the analysis using the PD analysis set will only include data that was measured ≤ 7 days after the treatment was stopped, i.e. data longer than 7 days after treatment discontinuation will be excluded. For individual figures using the PD analysis set all the data will be displayed but the lines will be solid up to the treatment discontinuation + 7 days and for subsequent time points the line should be dotted, i.e. the data that is excluded from the summary stats/analysis should be presented dotted.

If a subject took a prohibited medication then a footnote will be added to detail this in all PD outputs to explain that data after the usage may be affected by the medication.

6.1.3.3 Supportive analyses

The supportive analysis will be based on a longitudinal mixed model of change from baseline in ESSPRI as a function of baseline ESSPRI, baseline intake of steroids (yes/no, which is a stratification factor for the randomization), treatment, time (days from first treatment) as a continuous variable (linear and quadratic terms), interaction between treatment and time, as well as a random intercept, random slope and random quadratic effects by subject to account for within-subject correlations.

An unstructured covariance matrix for the random effects will be fitted along with an independent error matrix. The difference between active treatment and placebo in change from baseline in ESSPRI at study week 13 will be estimated from the model and presented with 80% and 95% confidence intervals (estimates will also be provided corresponding to the other visits where ESSPRI was assessed). Simpler models will also be considered in case the pre-specified model does not fit the data well.

Simpler models may be considered, including simpler covariance structures. If the time course does not appear to be quadratic, time may be modelled as a categorical variable.

The following criteria will be considered indicative of treatment efficacy:

- Statistically significant decrease in ESSPRI at week 13 visit on treatment compared to placebo (at one-sided 10% level)
- Estimated mean reduction in ESSPRI at week 13 visit for CDZ173 of 1 point or more than for placebo

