11.4.2 Statistical model, hypothesis, and method of analysis

It is assumed that the ESSPRI will follow an approximately normal distribution. If this assumption appears not to be met, alternative statistical analysis methods may be applied. These will be described in the Reporting and Analysis Plan (RAP).

The primary efficacy analysis will be based on a longitudinal mixed model of ESSPRI as a function of baseline ESSPRI, baseline intake of steroids (yes/no, which is a stratification factor for the randomization), treatment, time as a continuous variable (linear and quadratic terms), interaction between treatment and time, as well as a random intercept, random slope and random quadratic effects by subject to account for within-subject correlations. An unstructured covariance matrix for the random effects will be fitted along with an independent error matrix. The difference between active treatment and placebo in change from baseline in ESSPRI at study week 13 will be estimated from the model and presented with 80% confidence intervals. Simpler models will also be considered in case the pre-specified model does not fit the data well.

The following criteria will be considered indicative of treatment efficacy:

- Statistically significant decrease in ESSPRI at week 13 visit on treatment compared to placebo (at one-sided 10% level)
- Estimated mean reduction in ESSPRI at week 13 visit of 1 point or more than on placebo (see [Section 3.2](#))

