11.6 Sample size calculation

A total of approximately 27 patients will be recruited into the study. Patients will be randomized in a 2:1 ratio to either CDZ173 (n=18) or placebo (n=9) treatment groups. This number is based firstly on the assumed treatment effect in the primary endpoint ESSPRI and secondly on an assumed drop-out rate of 10% (i.e. 3 patients).

With 24 patients for the analysis of the primary efficacy variable (16 in the CDZ173 treated group and 8 in the placebo group), the study would have around 10% chance of having a false-positive result, i.e. of meeting both efficacy criteria when the true difference between CDZ173 and placebo is zero ESSPRI points.

The power of the study is 86% (when the true difference between CDZ173 and placebo is 2 points in ESSPRI).

The criteria for success are assumed to be the efficacy criteria defined in [Section 11.4.2](#).

These calculations assume that the change from baseline in ESSPRI is approximately normally distributed with a standard deviation of 2. This estimate of the standard deviation is based on a study of rituximab in patients with pSS ([Meiners et al 2012](#)).

The calculated numbers come from simulations done in R version 3.2.2.

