6.1.3 Statistical model, assumptions and hypotheses

It is assumed that the ESSPRI will follow an approximately normal distribution.

A positive sign of therapeutic effects will be considered to be a reduction of at least 1 point in the change from baseline between CDZ173 and placebo with a moderate level of evidence. Additionally there should be a high level of evidence that is a difference between CDZ173 and placebo. These criteria will be evaluated by calculating Bayesian posterior probabilities as follows:

$\Pr(\theta_{\text{CDZ173,13w}} - \theta_{\text{placebo,13w}} < 0 \mid \text{data}) > 90\%$ and

$\Pr(\theta_{\text{CDZ173,13w}} - \theta_{\text{placebo,13w}} < -1 \mid \text{data}) > 50\%$

where θ means change from baseline in ESSPRI at 13 weeks.

It is assumed that Y_{ijt} , the observed change from baseline in ESSPRI for subject i receiving treatment j (CDZ173 or placebo) at time t , follows a normal distribution $N(\theta_{jt}, \sigma^2)$. It is further assumed that θ_{jt} follows a standard non-informative prior Normal distribution, $p(\theta_{jt}, \sigma^2) = 1/\sigma^2$.

The statistical model will be a repeated measures model fitting terms for treatment by timepoint and baseline by timepoint using the SAS procedure PROC MCMC. Estimates of the difference between CDZ173 and placebo at each timepoint will be derived from this model and presented together with 95% credible intervals. The estimates of the posterior probabilities of the efficacy criteria being met will be provided.

Patients with missing ESSPRI at baseline will not be included in the analysis. Patients with missing data at one or more timepoints post baseline will be included in the analysis. The planned model assumes that missing values are missing at random. The reasonableness of this assumption will be checked during the blinded review of the data and if necessary further methods may be applied.

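### Protocol and SAP name different primary ESSPRI analyses, and the SAP attaches a success rule to each without saying which one decides

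*SAP*

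**What the plan says.** **Protocol 11.4.2.** "The primary efficacy analysis will be based on a longitudinal mixed model of ESSPRI as a function of baseline ESSPRI". The other terms are baseline steroid intake (the randomisation stratum), treatment, linear and quadratic time, a treatment-by-time interaction, and random intercept, slope and quadratic effects. Success has two parts: one-sided significance at 10%, and "Estimated mean reduction in ESSPRI at week 13 visit of 1 point or more than on placebo".

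**Protocol 11.6.** The false-positive rate of around 10% and the power of 86% at a true 2-point difference are tied to that rule: "The criteria for success are assumed to be the efficacy criteria defined in" Section 11.4.2.

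**SAP 6.1.3, under the primary objective.** "The statistical model will be a repeated measures model fitting terms for treatment by timepoint and baseline by timepoint using the SAS procedure PROC MCMC". There is no steroid term. The prior is flat. The success rule is a posterior probability above 90% that the difference is below 0, and above 50% that it is below -1. The section adds: "The estimates of the posterior probabilities of the efficacy criteria being met will be provided".

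**SAP 6.1.3.3, headed as supportive.** The protocol's mixed model reappears, followed by "The following criteria will be considered indicative of treatment efficacy" and the same two criteria as in protocol 11.4.2.

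**SAP 1.1** presents the SAP as implementing the analysis planned in the protocol. SAP 7.1.2 does flag a different departure from the protocol (the PK-QT model). The visible text flags nothing for ESSPRI. The interim and first-interpretable-results sections are redacted, and nothing is inferred from them.

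**The concern.** The study is a proof of concept meant to inform further development, so its efficacy rule should be unambiguous. As written, the two documents disagree on which model is primary, and the SAP holds two complete success rules for one endpoint at one visit.

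The models are not the same analysis in two notations. One adjusts for the stratification factor and the other does not. One imposes a shape on time and the other treats visits as categories. One has subject-level random effects, while the other states a single variance and no within-subject correlation. They can therefore reach different verdicts on the same data, and nothing says which then stands.

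The permissions in protocol 11.4.2 do not cover the switch. It allows other methods in the analysis plan if normality appears not to hold, but SAP 6.1.3 still assumes normality. It allows simpler models if the fit is poor, which is not a reason to pre-specify a different framework and decision rule.

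**Working it through.** **1. Reproduce the plan's figures.** Inputs from protocol 11.6: 16 and 8 patients analysed, SD 2, true difference 0 or 2. The one-sided 10% level is from 11.4.2.

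- SE = 2 × √(1/16 + 1/8) = 0.866.
- Difference needed for significance: 1.2816 × 0.866 = 1.11 (normal), or 1.3212 × 0.866 = 1.14 (t, 22 df). Both exceed 1, so the 1-point criterion rarely binds.
- Power at 2 points: Φ(2/0.866 − 1.2816) = Φ(1.028) = 84.8%. The joint false-positive rate is 10.0%.
- With an estimated SD, simulating both criteria gives 83.2% power and 9.5% false positives.

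These are close to the stated 86% and around 10%.

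**2. Does the SAP rule behave differently in that setting?** With the flat prior, the posterior for a two-sample difference d is t with 22 df, centred at d with scale SE.

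- Pr(difference < 0) > 90% is the same as d/SE < −1.3212, which is the one-sided 10% test.
- Pr(difference < −1) > 50% is the same as d < −1.

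In 400,000 simulated trials the two rules never disagreed (both 9.5% and 83.2%). Any difference between the rules therefore comes from the models, not from the Bayesian wording.

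**3. Apply the rules to the repeated-measures models.** From the documents: 16 and 8 patients, SD 2, ESSPRI at Days 29, 57 and 85 (protocol Table 8-1). Assumed, because the documents give no figures: between-visit correlation of changes 0.3-0.9, baseline-change correlation 0 or −0.4, half of patients on steroids, a constant or linear effect, no dropout, and a least-squares approximation to both models. There were 4,000-6,000 trials per cell, so the simulation standard error near 10% is at most √(0.1 × 0.9/4000) = 0.5 points.

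The interaction in the mixed model can be read as linear time only, or as linear plus quadratic. Results with correlation 0.5, baseline correlation −0.4, a constant effect and unstructured covariance in both models:

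| | Linear interaction | Linear + quadratic |
|---|---|---|
| No effect: SAP rule alone | 9.8% | 9.8% |
| No effect: mixed-model rule alone | 9.8% | 9.6% |
| No effect: either rule met | 12.0% | 10.4% |
| No effect: rules disagree | 4.5% | 1.5% |
| 2-point effect: rules disagree | 6.8% | 2.0% |

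Over all cells, each rule alone gave 8.6-10.4% false positives and 81.5-89.6% power. Either rule gave 9.6-12.6% and 82.4-91.6%. A separate run with other correlations put the lower end of the either-rule rate at 9.5%. Compared with the larger of the two single-rule rates, the second route added between 9.8 − 9.4 = 0.4 points and 12.6 − 10.0 = 2.6 points. Disagreement was roughly 1-7% of trials.

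**4. How firmly is the mixed model fixed?** An unstructured 3 × 3 random-effects matrix has 6 parameters, and the residual variance makes 7. Three post-baseline visits at nominal days supply a covariance matrix with 3 × 4/2 = 6. Some simplification is therefore likely, and SAP 6.1.3.3 leaves its form open.

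**The case against.** - **The labels already rank the models.** One sits under the primary objective and the other is headed supportive. A reader might infer from the repeated criteria that meeting either rule is enough for a positive result. The documents do not say that. The ranking is reasonable to infer, and it limits the risk. What remains is that a supportive analysis still carries its own statement of efficacy, while the protocol calls that same analysis primary.
- **The planning figures still apply.** A reader might infer that 10% and 86% are wrong for the SAP's rule because they cross-refer to the protocol's criteria. Step 2 does not support that. The inputs listed in protocol 11.6 contain no visit, correlation or steroid assumption, and on those inputs the two rules coincide. This part of the objection stands.
- **The inflation depends on modelling choices.** This also stands. With a quadratic interaction the added risk is about a point or less. Either-rule rates of 13-14% can be obtained by letting the SD rise from 1.5 to 2 over the visits, but neither document contains that pattern. The Bayesian rule alone, read with a common variance, then already gives about 11%, so much of the excess is not due to having two rules.
- **The study is non-confirmatory.** True, and it lowers the stakes. It does not settle which analysis decides.

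**Conclusion.** The inconsistency is real and can be read directly from the text: two primary models, two success rules, no stated precedence and no recorded change. The deciding SAP model also omits the factor used to stratify randomisation.

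The consequence is modest. Under SD 2 and the assumed correlations, accepting either rule gives about 9.5-12.6% false positives against about 9-10% for one rule, and the verdicts differ in roughly 1-7% of trials. These ranges rest on assumed visit correlations, complete data and approximate model fits. They do not show that the plan intends either rule to suffice, or that the figures in protocol 11.6 fail for the Bayesian rule.

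**What to change.** In the SAP, before the database is locked and unblinded:

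1. State which single model and rule decides efficacy, and record this as a change from protocol 11.4.2 (or restore the protocol model).
2. Delete the bulleted efficacy criteria from the other analysis and report it as a sensitivity analysis, with estimate and interval only. The 80% interval promised in the protocol is already planned for the mixed model in SAP 6.1.3.3.
3. Include baseline steroid use in the deciding model.
4. Note the false-positive rate and power of that one rule. A short statement that the protocol 11.6 figures carry over approximately would do if the flat-prior rule is kept.

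The cost is a few sentences of SAP text and a small simulation. The downsides are that the second analysis can no longer be cited as meeting a success rule, and that one more covariate is fitted in a trial of about 24 analysed patients.

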6.1.3.4 Graphical presentation of results

Lsmean (SE) and individual profiles will be produced by treatment and time.

6.2 Secondary objectives

6.2.1 Variables

Secondary efficacy variables supporting the secondary objectives are:

- Change from baseline in ESSDAI
- Change from baseline in SF-36 for both physical and mental component
- Change from baseline in MFI
- Change from baseline in Physician and Patient VAS of global disease activity

There was a scaling problem with the printed batch for the CRF sheets for the VAS scale in Hungary. The line that is printed and which is marked by either the patient or the physician should be 100mm long, but in the Hungarian site both VAS scales only measured 95mm therefore both VAS scales for the Hungarian site will be transformed by multiplying by 1.053 to get comparable results to the German site.

In the listings both the actual measurement and the value based on a length of 100mm will be presented with the transformed results based on a length of 100mm used in all other VAS outputs.

The key timepoint is the week 13 visit.

6.3 Exploratory objectives

Corporate Confidential Information

Corporate Confidential Information

Corporate Confidential Information

7 Statistical methods for safety and tolerability data

7.1.1 Variables

Adverse events, vital signs (blood pressure, pulse rate, body temperature), ECG intervals, laboratory measurements, as well as subject demographics, baseline characteristics, and treatment information.

7.1.2 Descriptive analyses

Subject demographics and other baseline characteristics

All data for background and demographic variables will be listed by treatment group and subject. Summary statistics will be provided by treatment group.

Relevant medical history, current medical conditions, results of laboratory screens, drug tests and any other relevant information will be listed by treatment group and subject.

Treatment

Data for study drug administration (rescue medication) and concomitant therapies will be listed by treatment group and subject.

Baseline concomitant medication related to pSS will be summarized by treatment group.

Summaries and listings of cumulative exposure to study drug (cumulative dose received over the treatment period) will be provided.

Heatmaps of exposure will be provided.

Vital signs

All vital signs data will be listed by treatment, subject, and visit/time and if ranges are available abnormalities (and relevant orthostatic changes) will be flagged. Summary statistics will be provided by treatment and visit/time.

ECG evaluations

All ECG data will be listed by treatment, subject and visit/time, abnormalities will be flagged. Summary statistics will be provided by treatment and visit/time.

In the protocol it was stated to use a longitudinal PK-QT model to check for concentration-dependent increase in QT. If this pooled analysis is done it will be presented in a separate report.

Clinical laboratory evaluations

All laboratory data will be listed by treatment, subject, and visit/time and if normal ranges are available abnormalities will be flagged. A separate listing is provided presenting all parameters in a subject with any abnormal values. Summary statistics will be provided by treatment and visit/time.

Adverse events

All information obtained on adverse events will be displayed by treatment and subject.

The number and percentage of subjects with adverse events will be tabulated by body system and preferred term with a breakdown by treatment. A subject with multiple adverse events within a body system is only counted once towards the total of this body system and treatment.

Heatmaps of neutropenia and rashes will be presented.

Liver and renal events will be listed and summarized using frequency tables.

Other safety evaluations

Immunogenicity

All immunogenicity results will be listed by subject and visit/time.

Infections

The frequency of infections will be tabulated.

7.1.3 Graphical presentation

Boxplots to visualize trends in longitudinal safety data (vitals, ECG, lab parameter) will be created.

8 Statistical methods for Biomarker data

Biomarker data (except for hypothesis-free platforms), change from baseline and percentage changes from baseline will be listed by treatment, subject, and visit/time.

Corporate Confidential Information

Summary statistics will be provided by treatment and visit/time. In the summary tables, the frequency (n, %) of values below the LLOQ and above the ULOQ, respectively, will be included.

Corporate Confidential Information

--	--	--
